9.0 Procedures Involved*

9.1 Describe and explain the study design.

This project adheres to PCORI methodological standards. Patient-reported outcomes measured with validated and reliable instruments will be the basis for us to compare the effectiveness of two distinct evidence-based models for culturally competent diabetes health promotion through research with two diabetes self-management programs that each currently serve a large Latino patient population from low-income households in Albuquerque, New Mexico. Data will be gathered at baseline, and 3, 6, and 12 months by paid PDCSs (PDCSs) from the target patient population who will be members of the research team. *A priori*, we believe patient populations for each program will be similar, yet we will compare sample characteristics and assess treatment differences after adjusting for possible population differences including the use of propensity scores in our statistical models to mitigate self-selection bias, possible confounding, and heterogeneity of treatment effects. Trickett's conceptualization of "cultural situated-ness" discussed above provides the theoretical framework for this study.^{37,38} We follow National Institutes of Health (NIH) standards for mixed method research set by Creswell and colleagues³⁹ in our "embedded mixed method" research approach, integrating data from quantitative and qualitative components of the study in an iterative fashion.³⁹ Our quasi-experimental research design with pre-/post-testing will accommodate the fact that we are working with existing programs at two sites and that we will recruit patients who enter those programs during the study.⁴⁰ Our sample size (N=240) and power estimates are based on realistic evaluation of effect size. We provide a detailed project timeline with specific deliverables that include scientific and engagement milestones. We have assembled a research team with the expertise and experience in patient-engaged research necessary to conduct the proposed study and we have an institutional infrastructure that supports our academic and community partnerships.

9.2 Provide a description of all research procedures being performed and when they are performed, including procedures being performed to monitor subjects for safety or minimize risks.

Data Collection.

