11.0 Data Management* and Confidentiality

11.1 *Describe the data analysis plan, including any statistical procedures.*

Descriptive statistics will be calculated to summarize patient characteristics. Means and standard deviations or medians and quartiles will be calculated for continuous variables and will be compared across site by ANOVA or Kruskal-Wallis test, depending on the distribution of the data. Frequencies and percentages will be calculated for categorical variables and will be compared with the chi-square test or Fisher's exact test, as appropriate. Significant differences will be noted and to adjust for possible confounding, those variables will be considered for inclusion as covariates in the analyses for the primary and secondary outcomes in addition to other clinically meaningful variables and their interactions. We expect patient characteristics to be similar across the two treatment sites; however, to control for potential differences in the populations, we will adjust for potential confounding covariates by using propensity scores to stratify subjects into groups based on the probability that they attended a particular treatment site given particular demographic characteristics including sex, age, primary language, level of education, nativity, and type of insurance. Patients will be grouped by quintile of propensity score for a total of five strata and each will be analyzed for the primary and secondary outcomes independently. Analyses will be performed in standard statistical software such as SAS 9.4, R 3.1, and/or Stata 14. Propensity score matching allows for causal inference in our non-experimental settings by selecting similar subsets of comparison units between treatment groups across a high-dimensional set of pretreatment characteristics.

We will complement our quantitative analyses by conducting a rigorous, disciplined, empirical analysis of data from key staff/provider interviews (Aim #1), patient/social support interviews and focus groups (Aims #1 & 2), and Patient Advisory Board interview transcripts.

PROTOCOL TITLE: Comparing Program Options for Latinos with Diabetes

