- 1.) Hypothesis: The CCM model will result in a larger decrease in percent A1c from baseline to 6 months with Cohen's f ES = 0.06 as compared to the DSMS. Previously published studies and institutional experience evaluating culturally competent diabetes management programs report changes in percent A1c with effect sizes of 0.01 to 0.06 in studies ranging in sample size per arm from 26 to 133.^{66,105-107}
- 2.) Hypothesis: The CCM model will result in a larger decrease in BMI from baseline to 6 months than DSMS with a clinically meaningful difference of 1.5 kg/m² between the groups (Cohen's f ES = 0.06).^{67,68}
- 3.) Hypothesis: Compared to DSMS, CCM will result in a larger decrease (by 3 points) in PHQ-9 scores from baseline to 6 months (Cohen's f ES = 0.06).¹⁰⁷⁻¹⁰⁹

Note: It is coincidental that the effect sizes (and power) are the same for each of the three secondary outcomes

Power Calculations. We will recruit N=240 patient-social support pairs (n=120 per site) with anticipated 20% attrition to obtain complete data on at least n=96 per site. Comparing response changes on the DKQ, PAM-13, and DHQ-9 from baseline to 6 months between the CCM to the DSMS, the two-sided Type I error rate was adjusted for the number of comparisons made (four comparisons for the co-primary outcomes) using a Bonferroni correction ($\alpha=0.0125$). The power analyses for detecting site differences among change scores were based on multiple linear regression models including demographic characteristics, participants' perceived cultural competence of providers (CAHPS-CC), and social supports' change scores on the DHQ, PAM-13, and DHQ-9 as covariates. We report Cohen's f effect sizes based on the regression method.^{110,111}

The power for the primary endpoints with n=96 per site and $\alpha=0.025$ are as follows:

- 1.) Change in DKQ summed score: $\Delta_{CCM-DSCS} = 2.2$ (SD = 3.8), power = 96%, Cohen's f effect size (ES) = 0.09
- 2.) Change in PAM-13 raw score: $\Delta_{CCM-DSCS} = 12.7$ (SD = 24.8), power = 85%, Cohen's f ES = 0.07

The power for the secondary endpoints with n=96 per site and $\alpha=0.017$ for comparing the CCM to the DSMS:

- 1.) Change in A1c: $\Delta_{CCM-DSCS} = -0.5$ (SD = 1.0), power = 84%, Cohen's f ES=0.06.
- 2.) Change in BMI: $\Delta_{CCM-DSCS} = -1.5$ (SD = 3), power = 84%, Cohen's f ES=0.06.
- 3.) Change in depression scores (PHQ-9): $\Delta_{CCM-DSCS} = -3$ (SD = 6), power = 84% Cohen's f ES = 0.06.

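### Section 11.1 specifies separate propensity-quintile analyses but credits causal inference to matching; one full-cohort method with a single overall site effect should be named, and the power statement tied to it

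*Combined protocol and SAP*

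**What the plan says.** Section 11.1 commits to stratification on the propensity score. The score is built from sex, age, primary language, education, nativity and insurance type. The strata are defined as follows: "Patients will be grouped by quintile of propensity score for a total of five strata". The outcome analyses are then run separately within every stratum, and no rule is given for combining the five results.

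The paragraph closes with its causal justification: "Propensity score matching allows for causal inference in our non-experimental settings by selecting similar subsets of comparison units between treatment groups". The document gives no matching ratio, caliper, replacement rule or handling of unmatched patients.

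Section 9.1 is less specific and refers only to "including the use of propensity scores in our statistical models". The A1c mixed model later in 11.1 lists its covariates without naming a propensity term.

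Section 11.2 recruits 120 patient–support pairs per site "with anticipated 20% attrition to obtain complete data on at least n=96 per site". Its power figures come from multiple linear regression with covariates. Neither propensity strata nor matching enters that calculation.

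**The concern.** Stratification can keep every patient and, once the strata are combined, estimates a site effect for the whole cohort. Matching that selects subsets can drop patients, and its estimate then describes only those who were matched. The causal claim is attached to a method that the operative sentences do not carry out, so the analysis population and the estimand are unclear.

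The procedure that is specified has its own gap. Five independent analyses give five small-sample site differences per outcome and no overall answer to the study question. The sample size supports one comparison of 96 with 96. It was not set for five smaller comparisons or for a matched subset.

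**Working it through.** **Inputs from section 11.2.** 120 per site less 20% attrition is 120 × 0.8 = 96. The A1c difference is 0.5 with SD 1.0, at two-sided alpha 0.017 and stated power 84%. BMI (1.5, SD 3) and PHQ-9 (3, SD 6) have the same ratio of 0.5 and the same stated power.

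**Reproducing the plan's figure.** Normal approximation: power = Φ(Δ / (SD·√(2/n)) − z₁₋α/₂). With n = 96, 0.5 / √(2/96) = 3.464 and z = 2.387, so power = Φ(1.077) = 85.9%. The noncentral t gives 85.3%. Both are within 2 points of 84%, so the stated figure belongs to a single unstratified comparison of 96 with 96.

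**Quintiles analysed independently.** 192 / 5 = 38.4 patients per stratum, or about 19 per site if balanced. For A1c, 0.5 / √(2/19) = 1.541, so power = Φ(1.541 − 2.387) = 19.9%, or 18.3% by noncentral t. A 10 v 28 split gives 14–15%. For the primary DKQ outcome (2.2, SD 3.8, alpha 0.025), a balanced stratum has 30–32%. None of these figures includes a correction for five tests per outcome.

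**If patients were matched.** The documents give no match rate, so this part is conditional. By the normal approximation, 84% power needs 92 pairs and 80% needs 84 pairs, out of a maximum of 96.

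To see what a matching rule might leave, assume 96 per site, normal logit scores with a mean shift of √2·Φ⁻¹(AUC), 1:1 matching without replacement and a caliper of 0.2 SD of the logit score. Figures are simulated means, with noncentral t power for A1c, BMI and PHQ-9:

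| Site separation (AUC) | Greedy: pairs | Power | Optimal: pairs | Power |
|---|---|---|---|---|
| 0.50 | 81 | 78% | 87 | 81% |
| 0.60 | 76 | 75% | 82 | 78% |
| 0.70 | 66 | 68% | 70 | 71% |
| 0.80 | 52 | 55% | 55 | 58% |

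DKQ power at the greedy counts of 76, 66 and 52 pairs is about 90%, 85% and 75%.

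**Fair comparator.** Adjusting for the score in the full cohort also costs precision when the sites differ. Taking effective n = 96 × (1 − r²), with r² the share of site variation explained by the score and residual SD held at 1.0:

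| AUC | r² | Effective n per site | A1c power |
|---|---|---|---|
| 0.60 | 0.03 | 93 | 84% |
| 0.70 | 0.12 | 84 | 80% |
| 0.80 | 0.26 | 71 | 71% |

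At AUC 0.80 the extra loss from greedy matching is therefore from about 71% to 55%.

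**The case against.** The strongest reply is that this is loose terminology. The sentences that commit the analyst to action all describe stratification. The matching sentence is a general rationale with no algorithm, and neither the mixed model nor the power section uses matching. The wording in 9.1 is a summary that fits stratification, so it is not a competing third method. The plan also says "We expect patient characteristics to be similar across the two treatment sites", which would limit any loss from matching.

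Most of this stands. A reader might infer that the study will fall short of 96 per site and 84% power. The documents do not support that: no matched analysis is planned, no match rate is given, and if 95% of completers were matched (91 pairs) power would be 83.8% by the normal approximation. The 84% also applies only to the three secondary endpoints; primary power is stated as 96% (DKQ) and 85% (PAM-13).

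Two things survive. Similar sites do not by themselves protect the sample size, because with equal arms there is no reserve pool: under the greedy rule above, identical score distributions still leave only about 81 pairs. Some separation is also plausible, since the score includes language and insurance type, and section 2.2 describes One Hope as emphasising Spanish and offering access regardless of ability to pay. Nor does the terminology defence address the missing rule for combining strata.

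**Conclusion.** The inconsistency is real, and nothing else in the document resolves it: the causal claim in 11.1 rests on a method other than the one specified, and the power in 11.2 is calculated for neither. The firmer numerical consequence concerns the procedure as written. About 19 patients per site per stratum, assuming balanced strata, gives about 18–20% power for A1c and no overall site effect. The loss from matching is conditional on the rule and on overlap: about 78% to 55% power for the secondary endpoints under greedy matching at AUC 0.50 to 0.80, and about 81% to 58% under optimal matching with the same caliper. It shows why the sentence should not stand unqualified; it does not predict a failure of the study. This should be corrected before analysis, so that the population and estimand are not chosen with results in view.

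**What to change.** In section 11.1, delete or correct the matching sentence and replace the independent stratum analyses with one primary propensity method in the full enrolled cohort, with no patient dropped for lack of a match. Two suitable choices are a single pooled, stratum-weighted site effect across the quintiles, or the score as a covariate in the outcome model. Attach the causal wording to that method, and carry the same method into 9.1 and the outcome models.

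In section 11.2, state that "to obtain complete data on at least n=96 per site" refers to that analysis and base the power on it, including some loss of precision if the sites differ. Any matched analysis should be labelled a sensitivity analysis, with its matching rule and n reported.

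The cost is wording and a revised power statement; recruitment, data collection and patient care are unaffected. The downside is small: full-cohort adjustment leans on the score model where overlap is thin, which a matched sensitivity analysis would help to show, and it loses some precision if the sites differ strongly.

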Eligibility Screening: potential participants who agree to being screened for eligibility will be contacted by a member of the research team and asked the eligibility screening questions, including requesting information about a potential social support partner. The patient participant will be offered the opportunity to contact their potential social support partner to inform him or her that a research team member will be in contact to conduct an eligibility screening. When the patient partner gives permission to contact the potential social support partner, a member of the research team will contact the potential social support partner and conduct the eligibility screening. If both the patient participant and his or her social support partner are deemed eligible, baseline data collection appointments will be scheduled with both participants. The information collected during the eligibility screening will be hand-written on an Eligibility Screening form and given to the Patient Engagement Coordinator, who will enter it into REDCap in the Eligibility Screening project. The Patient Engagement Coordinator will then create a record for the participant in the PCORI Diabetes Project in REDCap and assign a participant ID (PID) to the participant. The Patient Engagement Coordinator will keep a master list of the participants' names and PIDs both electronically and in hard copy. The electronic copy will be saved on her password-protected laptop, which is stored in a locked cabinet at One Hope when not in use. The hard copy will also be stored in a locked cabinet at One Hope.

Data Collection: at the baseline data collection appointment, the PDCS will collect and enter contact and demographic information into separate data collection instruments in the PCORI Diabetes Project in REDCap. At the baseline and all three follow-up appointments, the PDCSs will also administer the survey instrument to the participants, responses to which will be entered into a third data collection instrument in the same project. The PDCSs will also collect BMI measurements (weight and height) and draw blood for A1c testing at the baseline and all follow-up appointments and will collect a hair sample at the baseline and six-month follow-up appointment. The BMI measurements will be entered into a fourth data collection instrument in the PCORI Diabetes Project by the PDCS during

PROTOCOL TITLE: Comparing Program Options for Latinos with Diabetes

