Programmatic assessment. We will inventory each program regarding program design, size, structure, operation, and theoretical/philosophical orientation; professional qualifications/training of program providers; activities or resources available through the programs; strategies in place for Spanish language use or acceptance, inclusion of social supports and family, accommodation of challenges created by patients' limited socioeconomic circumstances, and the inclusion of stress management techniques; and data on referrals to the program, sign-ups, participation, no-shows, and attrition. We will conduct up to 36 interviews with key staff and/or providers (6/year x 2 sites x 3 years) to obtain their perspectives on implementation of the programs during the period of the study. Interview questions will be semi-structured to allow participants to contribute to the direction of the interview in relation to issues and ideas that they consider to be most relevant and important. Interviews will be audio-recorded and transcribed. We will assess patient and social support perceptions of the program interface using a cultural competence survey^{88,89} that asks about physician bias, inter-cultural understanding, respectful interactions, language barriers, experiences of discrimination, and issues of trust. Administration of the survey is described in the paragraph immediately below this one. The cultural competence portion of the survey will not be administered at baseline as the participant will not yet have experience with which to rate the program. To gather qualitative information, we will include questions on programmatic interface in interviews and focus groups with patients and social supports that are described two paragraphs below.

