Surveys. We will hire four individuals from the population of study to work as PDCSs. The PDCS at each site will administer a survey orally to all patient and social support participants at baseline (when they enter the study), with follow-up at 3, 6, and 12 months. The survey will consist of questions from or modified from four validated and reliable tools: 1.) The *Consumer Assessment of Healthcare Providers and Systems Cultural Competence Set (CAHPS-CC)*^{88,89} [as part of the programmatic assessment discussed in the preceding paragraph—will be administered at 3, 6 and 12 months only]; 2.) The *Diabetes Knowledge Questionnaire (DKQ)*^{51–53,112}; 3.) The *Patient Activation Measure (PAM-13)*^{55–62,113}; and 4.) The *Patient Health Questionnaire 9 (PHQ-9)*.^{70–73}

Interviews with patient and social support participants. We will conduct 72 interviews with patients and social supports (12/year x 2 sites x 3 years). Following Guest, Bunce and Johnson,¹¹² and [name]'s own experience with interview data, we believe that data sets of 12 interviews per site per year will capture a sufficient range of responses to achieve

PROTOCOL TITLE: Comparing Program Options for Latinos with Diabetes

thematic saturation. Our sampling frame for each set of 12 interviews will include six patients and six social supports. Interviews will be conducted with the social supports who correspond to the six patient interviewees. Interviews will follow the same format described in the programmatic assessment above. Spanish transcripts will be translated into English for analysis.

Focus groups. We will conduct 12 focus groups (2/year x 2 sites x 3 years). Focus group participants will be distinct from those recruited to participate in the interviews described in the preceding paragraph. Focus groups will include six distinct participants each (three patients and their corresponding social supports per focus group x 12 focus groups = 72 participants). The focus group questions and protocol will be an adaptation of that described above for the interviews.

Physical Measures. These measures will be obtained from patients at baseline with follow-up at 3, 6, and 12 months:

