Hair cortisol: We will measure patient stress levels by testing hair samples to identify circulating levels of cortisol as a biological marker for chronic stress. Hair will be gathered from patients only and not from social supports, and will only be gathered at two timepoints: baseline and 6 months. Hair cortisol is an emerging valid biomarker for chronic stress.⁹² Alterations in cortisol have been uniformly identified in various forms of chronic stress.⁹³⁻⁹⁷ Cortisol inhibits glucose uptake, and as an anabolic hormone, it activates glucose production. Cortisol levels are altered in people with chronic stress (sometimes low, but most often higher than normal). Chronic levels of cortisol can be measured in hair, similar to chronic levels of glucose measure in A1c. Recently, measurements of cortisol levels in hair have proven useful to determine the long-term effects of stress.^{83,92,99,100} Typical hair growth rate is 1 cm per month. Thus, by testing 1 cm of 100-150 strands of hair from the crown of the head (a thickness less than that of a pencil), an average cortisol level over the corresponding month can be obtained. This measure will provide important novel data because we believe that a culturally competent diabetes self-management program would help people deal with not only the stress of having diabetes and feeling like it is a death sentence by learning everyday self-management strategies, but also because having a feeling of connectedness through a health promotion program can provide emotional support and relief and thereby decrease the stress and decrease insulin resistance (which is the pathophysiological basis of diabetes type 2 in most cases).

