10.0 Data and Specimen Banking*

10.1 *If data or specimens will be banked for future use, describe where the specimens will be stored, how long they will be stored, how the specimens will be accessed, and who will have access to the specimens.*

Hair samples are being collected as part of the data collection for this project. We are seeking funding to allow us to analyze the hair samples. Hair samples can be stored for up to two years before being analyzed. We will store hair samples in plastic bags in a cool, locked drawer in the office of the PI. The PDCS will gather the sample, wrap it in tin foil to keep the sample in a coherent bunch, place the foil-wrapped sample in a plastic bag, label it with the PID and give the bag to the Patient Engagement Coordinator. The Patient Engagement Coordinator will transfer the sample to the UNM Research Manager. When we obtain funding for the analysis, we will send the de-identified numerically labeled samples to the UNM lab of Co-I [name] for analysis. The names correlating with the ID will be kept in a locked drawer in the PI's office.

In general, we are committed to making our data available to other researchers to contribute to knowledge about cultural competence and diabetes self-management program models. Following the end of the study, the quantitative data will be de-identified within nine months and made available to PCORI and to researchers by request. Interview and focus group transcripts will not be shared because this data will have been gathered from a small sample that represents a small community and will contain a large amount of personal information that would identify the participant.

The UNM CTSC Bioinformatics Data Warehouse will assist us in assuring all the quantitative data is properly de-identified at the end of the project. Blood samples will be destroyed following analysis. Hair samples will be

PROTOCOL TITLE: Comparing Program Options for Latinos with Diabetes

stored until they can be analyzed. After analysis, any left over hair will be stored until we are certain that we had enough of a sample for testing. The data gathered for the A1c analysis, BMI, and hair cortisol will include the participants' study ID but no personally identifying information that could be linked to the participant.

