We will create a database with all interview and focus group transcripts. We will conduct a theory-driven qualitative content analysis. We will read through transcripts to identify conceptual categories and patterns related to specified domains of inquiry, create a qualitative codebook, and develop conceptual summaries for each transcript. Following review and summary, we will code transcripts for systematic themes and sub-themes within the domains. We will explore interconnections between theme categories and develop a holistic interpretation of the data.

Statistical Analysis Aim 3. We will conduct analyses to assess successful patient management of their diabetes (Aim #3), our secondary outcomes, by measuring their A1c from blood samples drawn, BMI calculations, cortisol from hair samples, and PHQ-9 scores obtained at baseline, 3, 6, and 12 months. Clinical analysis of blood samples will use A1c tested on whole blood as described previously. Change in A1c over the four time points in each of the diabetes self-management program models will be evaluated by fitting a linear mixed model to A1c with the primary independent variable treatment site while adjusting for demographic covariates, social support and knowledge, the measures hair cortisol indicating stress levels, and participant and social support scores on the CAHPS-CC. An interaction between time and site will be included to explore how A1c scores change over time. For the secondary endpoint analysis, REML-adjusted least-squares mean estimates of change in A1c from baseline to 6 months post-intervention will be reported along with their 98.3% confidence intervals (the significance level includes a Bonferroni adjustment for three secondary outcomes). A model incorporating the 12 month time point will also be evaluated. BMI and depression scores will be analyzed similarly.

11.2 Provide a power analysis.

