3.) **Hair cortisol**: We will measure patient stress levels using testing of hair samples to identify circulating levels of cortisol as a biological marker for chronic stress. We will only gather hair samples from patient participants and not from social supports, and hair will only be gathered at two time points: baseline and six months. Cortisol is an insulin antagonist and may contribute to insulin resistance in diabetes type 2. The PDCS will use scissors to collect a pencil lead-width of hair from the crown of the head of patient participants. One centimeter of hair closest to the scalp will be used to measure hair to determine the average cortisol level over the previous month. The hair will be stored in a plastic bag in a cool, locked drawer in the office of the PI. We are seeking to obtain funding from the CTSC to analyze hair samples from this project. Co-[name] will lead analysis of hair samples. In preliminary studies [name]'s group has found that more than 90% of subjects agree to hair samples. Hair will be pulverized in a Retsch Mixer Mill Type MM 400 100-240V 50/60HZ and, extracted in methanol overnight, dried and resuspended in buffer. Cortisol concentration is measured by an immunoassay or by high-pressure liquid chromatography. Control samples containing specific amounts of cortisol are provided by the vendor with each assay kit, and we also use an internal control. We will use an automated colorimetric 96-well plate reader to measure the results. Cortisol levels are compared with average levels from normal subjects. The [name] group has determined the normal range of human cortisol hair levels. Control measurements are done with random hair samplings from non-diabetic individuals combined and used as a standard for all measurements. Measurements are compared to the average and determined to be within or outside normal limits. Comparison to normal limits is the standard method for reporting clinical pathology laboratory measurements diagnostically.

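### Section 11.1 adjusts the A1c, BMI and PHQ-9 models for hair cortisol and CAHPS-CC, which are not measured at every visit and, after baseline, lie on the hypothesised causal pathway; their form and cortisol's role need to be fixed

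*Combined protocol and SAP*

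**What the plan says.** The Aim 3 paragraph of section 11.1 builds the secondary outcomes from four measures (A1c, BMI, hair cortisol, PHQ-9) and ends the list with a shared schedule: "cortisol from hair samples, and PHQ-9 scores obtained at baseline, 3, 6, and 12 months". A1c is then analysed over four time points in a linear mixed model with site, a time-by-site interaction, and adjustment for demographics, social support, knowledge, hair cortisol, and the CAHPS-CC scores of patient and support person. The reported contrast is the change from baseline to 6 months with a 98.3% interval, and the text adds that "the significance level includes a Bonferroni adjustment for three secondary outcomes". A model that brings in month 12 is also planned. BMI and depression scores are to be handled in the same way.

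The collection sections differ. In section 9.2 the lead-in to the physical measures says "These measures will be obtained from patients at baseline with follow-up at 3, 6, and 12 months", but the hair entry narrows this: hair "will only be gathered at two timepoints: baseline and 6 months". The data-collection text in 9.2, repeated in 25.3, says that the data collectors "will collect a hair sample at the baseline and six-month follow-up appointment", and section 11.5 states that "hair will only be gathered at two time points: baseline and six months". For CAHPS-CC, section 9.2 says "The cultural competence portion of the survey will not be administered at baseline", because patients have no experience of the programme at that point; it is given at 3, 6 and 12 months. On the assay, section 10.1 says "We are seeking funding to allow us to analyze the hair samples". Section 11.2 names A1c, BMI and PHQ-9 as the secondary outcome measures and powers each at alpha 0.017.

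**The concern.** There are three linked problems. First, 11.1 gives cortisol a schedule that the study does not follow, and uses it both in the list of secondary outcomes and as a covariate for one of them. Second, the confirmatory secondary model contains two covariates that are absent by design at some visits, with no statement of whether they enter as one value per patient or visit by visit. Third, CAHPS-CC has no baseline form at all, so any single value per patient is a rating made after exposure to the programme being compared.

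The site contrast on all three powered secondary outcomes is at stake. Depending on how an analyst fills the gap, the same text yields a model that cannot estimate the stated endpoint, or one that can but answers a different question from the total effect of the programme.

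**Working it through.** **Visit availability** (sections 9.2, 11.5 and 25.3)

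| Variable | Baseline | 3 m | 6 m | 12 m |
|---|---|---|---|---|
| A1c | yes | yes | yes | yes |
| Hair cortisol | yes | no | yes | no |
| CAHPS-CC | no | yes | yes | yes |

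Section 11.2 expects 96 completers per site, so 2 × 96 = 192 patients and 192 × 4 = 768 patient-visits. Without imputation:

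| Form of covariates | Complete visits | Patient-visits | Baseline-to-6-month change |
|---|---|---|---|
| Baseline cortisol, fixed; no CAHPS-CC | 4 of 4 | 768 | estimable |
| Cortisol by visit only | 0, 6 (2 of 4) | 384 | estimable |
| CAHPS-CC by visit only | 3, 6, 12 (3 of 4) | 576 | not estimable |
| Both by visit | 6 (1 of 4) | 192 | not estimable |
| Both as one post-baseline value per patient | 4 of 4 | 768 | estimable, but conditions on the pathway |

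If month 12 is left for the additional model, the base is 192 × 3 = 576. Cortisol by visit then covers 2 of 3 visits, and both by visit still leaves only month 6.

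**Pathway.** Section 9.2 (hair cortisol) expects a culturally competent programme to lower stress and, through that, insulin resistance. Sections 1.2, 2.2 and 11.2 attribute the expected advantage of one programme to its better cultural and contextual fit, and CAHPS-CC measures patients' perception of such fit. If a share p of the planned A1c difference of −0.5 runs through these variables, then in the simplest linear case the adjusted site coefficient targets −0.5 × (1 − p). Unmeasured common causes of the mediator and A1c can add bias in either direction. The documents give nothing from which to estimate p.

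**Outcome count and alpha.** The plan's own figures come first. For three outcomes, 0.05/3 = 0.0167 and 1 − 0.0167 = 98.3%, as stated. Power for A1c uses a difference of 0.5, SD 1.0, n = 96 per site and two-sided alpha 0.017 (two-sided is stated for the primary comparisons and assumed here):

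- Power ≈ Φ(0.5/√(2/96) − z₀.₉₉₁₅) = Φ(3.464 − 2.387) = 85.9%. The noncentral t gives 85.35%. The plan states 84%.
- BMI (1.5/3) and PHQ-9 (3/6) have the same standardised difference of 0.5, so the same power.
- With cortisol as a fourth outcome, alpha is 0.05/4 = 0.0125, the interval is 98.75%, and power is 83.3% (normal) or 82.6% (t).

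The plan's power is thus matched within two points by an unadjusted two-group comparison. It does not depend on precision gained from cortisol or CAHPS-CC.

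**Missing cortisol.** Section 9.2 reports that more than 90% of subjects agreed to hair sampling in preliminary studies, so expected refusal is under 10%. At an assumed 90% availability, 0.9 × 96 = 86.4, or 86 per site, and complete-case A1c power at alpha 0.017 is 80.6% (t). If the assay is never funded, availability is zero and a model with a cortisol term cannot be fitted. Section 10.1 also limits storage before analysis to two years. On the recruitment table, the first samples (February 2017) reach that limit in February 2019, with 12-month visits scheduled to April 2019.

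**The case against.** The strongest reply is that nothing in 11.1 prescribes visit-by-visit covariates or listwise deletion. Baseline cortisol and one CAHPS-CC value per patient would lose no visit structurally. Section 11.2 lends this some support: its change-score regressions have one row per patient and already include CAHPS-CC. This stands, and the loss of visits is therefore conditional. It does not dispose of the point, because a person-level CAHPS-CC score can only be post-baseline, and that leads to the pathway problem.

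The missing-data text in section 13.3 offers multiple imputation as an option. It does not address covariates absent by design, and no patient has CAHPS-CC at baseline, or cortisol at 3 or 12 months, to inform an imputation.

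A reader might infer three stronger things that the documents do not support:

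- *Two-visit hair sampling by itself makes the A1c model lose most of its visits.* Cortisol by visit costs two of four and keeps exactly the two visits of the stated contrast. CAHPS-CC removes baseline.
- *The Bonferroni count of three is wrong.* Section 11.2 defines, hypothesises and powers exactly three outcomes, and 98.3% agrees with that. Cortisol has no hypothesis, effect size or power, so the stray item is cortisol in the 11.1 list.
- *Hair refusal could cost more than a tenth of the sample.* Agreement above 90% means refusal below 10%.

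It is also fair to say that the funding gap is disclosed, and that it leaves the collection of A1c, BMI and PHQ-9 data untouched.

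**Conclusion.** The point holds as a defect of specification in the confirmatory secondary analysis. The schedule contradiction is certain: four visits for cortisol in 11.1 against two everywhere that hair collection is described. The covariate form is unspecified for cortisol and CAHPS-CC in all three secondary models. The consequence depends on the reading. Both by visit without imputation leaves 1 of 4 visits and no estimate of the baseline-to-6-month change. Post-baseline values per patient keep all visits, but can bias the site effect by conditioning on the plan's own mechanism, to a degree that the documents do not allow one to calculate. Only baseline cortisol escapes both problems, and it depends on unfunded assays.

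The count of three secondary outcomes, alpha 0.017 and the 98.3% intervals are sound once cortisol is labelled exploratory. Counting it as a fourth outcome would cost under three points of power. The pathway conclusion assumes that the study seeks the total effect of programme on outcome, which is how the hypotheses in 11.2 are worded.

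**What to change.** Before analysis:

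1. Correct 11.1 so that cortisol is measured at baseline and 6 months.
2. Label cortisol exploratory. Three secondary outcomes, alpha 0.017 and 98.3% intervals then stand.
3. Remove CAHPS-CC and post-baseline cortisol from the confirmatory A1c, BMI and PHQ-9 models, and use them only in exploratory mechanism analyses that state how each enters.
4. Make the covariate list in the power section, 11.2, match.
5. If the assay is funded, baseline cortisol may be kept as a fixed covariate in a sensitivity analysis. Say that this analysis is dropped if it is not.

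The cost is wording, with no new data. The confirmatory models give up any precision that these covariates would have brought, and the description of the power model in 11.2 must be revised. As shown above, the stated secondary power does not rest on that precision.
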